Before Covid-19 children in Greater Manchester were already experiencing waiting times of up to 12 months for dental treatment under GA, often leading to episodes of pain, time off school and repeat courses of antibiotics. According to the Commissioners within GM as of December 2021, there were 1779 children on the waiting list, 716 of whom have been waiting over 52 weeks. These figures show the continued pressure on the system with children waiting an unacceptably long time for treatment. These numbers are now decreasing with the implementation of CFDP, where this pathway is able to take new patients entering the referral system. The CFDPs have shown promising preliminary results with 50% of children seen within a CFDP. The dental commissioning team in GM are committed to increasing the number of CFDPs by reallocating existing funding. There is considerable interest in this type of scheme from other areas of the country in view of the national policy drivers supporting flexible commissioning; following the work in GM further regional pilots have been established this year (for a minimum of 6 months) in the South East of England lead by [name] (who has agreed to join our steering committee if the study is funded – further information is available in the letter of support from [name]). There has also been interest in our research proposal from Northern Ireland and Wales.

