While the pilot indicated promising results, with 50% of children being able to be seen within a CFDP, the long term impacts and health outcomes of the use of CFDP are unknown. There have also been concerns raised from some within the field that children treated within a CFDP may still require future intervention in a more specialist service, within a short period of time. If so, there would not be a reduction on the pressure seen on these services and the overall costs of this scheme would be higher than usual care. The proposed research is required to provide a robust, longitudinal evaluation of the CFDP pathway, building on the initial work from the pilots, which can strengthen the case for nationwide adoption if shown to be successful. Following a realist evaluation approach will also mean the research will provide evidence of what works, for whom and when. The project will provide evidence of long term outcomes (treatment required, pain, use of antibiotics) and a health economic evaluation which can be utilised by commissioners for future schemes. If a high proportion of children referred to specialist services can be treated at CFDPs, this model has the potential to improve access to care across the system. In particular, increased use of CFDPs could allow hospital/specialist services to focus on those in greater need. The implementation of an alternative pathway could allow those urgent cases, and cases for which a dental GA is unavoidable, such as medically compromised children and those with additional needs, to be seen sooner. It may also reduce the need for GA for some children if they are seen sooner than they would otherwise be seen along a traditional pathway.

Research objectives.

The aim of this research is to determine the performance of CFDP pathway compared to a traditional Specialist Paediatric Dental pathway on the longer term oral health and treatment outcomes for children referred to specialist care due to severe decay and the associated health economic costs.

Our primary and secondary research questions (and subsequent objectives/methods) are as follows:

Primary

- *Does treatment through a CFDP reduce treatment under General Anaesthetic when compared to the traditional pathway over a period of 2 years?*
 - Using GA data gained from Hospital Episode Statistics (HES)/Community Dental Service (CDS) records the team will assess the number of GAs carried out along each pathway for dental extraction.

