To determine the required sample size, the sample size calculation was based on a two-sample test for proportions. Results indicated that 354 participants per group, 708 participants in total, will allow a difference in proportions in the need for a GA from 25% to 15% to be detected with 90% power and a two-sided significance test at the 0.05 level. We anticipate that at least 10 clinics who are providing care under Child Friendly dental pathway and 10 clinics who are providing care under the usual Specialist Dental pathway will participate in the study.

The study sites are divided into two groups: Community Dental Services (CDS) and Child Friendly Dental Practices (CFDP) with an original planned sample size of 708 participants from both groups, or 354 per group **at the end of the study**. Due to low recruitment numbers from the CFDP group among the study sites, the remainder of the required sample size for the CFDP group will be supplemented with unconsented, **anonymised** data obtained from the dental referral management system, **the data will be from a similar timeframe** of the consented data collected in the CDS group obtained from the study sites.

In 2023, 230 patients were seen and treated within CFDP if the same number are seen and treated within 2024 this will provide data on 460 patients. As we would have a larger sample from the CFDP this would mean only 292 patients would need to be recruited from the CDS to reach a power of 90% to detect a difference in proportions in the need for a GA from 25% to 15%. This approach will allow the study to meet its target sample size and effectively address the research questions and objectives. Recruitment and numbers seen through CFDP will be closely monitored so that recruitment can end as soon as the minimum sample size is reached.

Inclusion / exclusion characteristics

Child aged 4-15 years only (cut-off 16th birthday)

Child resident in Greater Manchester

Child referred by general dental professional based in Greater Manchester

Child contact information complete i.e., age, contact address, telephone number, carer

Extractions requested and radiograph provided

Child medical history complete

Reason why treatment cannot be provided by referring dentist provided

Dental charting complete

Child with no or mild medical complexities

Child with no or mild behavioural complexities

Child presents with symptomatic teeth in one or two quadrants only

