Primary: The primary outcome, measures whether a child has had a dental extraction under General Anaesthetic two years after referral as indicated in electronic patient records (recorded through HES data or through CDS patient records).

Secondary: The secondary outcomes to be considered in this project include:

- Waiting time until first appointment
- Number of sessions of treatment
- Whether a child was successfully seen and treated. For this outcome success is defined as treatment completed by a dentist that results in a child being referred back to their own dentist or discharged, pain free.
- The number of extractions and restorations as reported in NHS BSA data
- The courses of antibiotics taken during wait and treatment
- Participants referred back into the specialist pathway within two years of referral.
- Dental pain experienced by a child
- Participants views of their treatment and engagement with the dental profession (follow up of dental appointment) as indicated by the responses to the text message. Questions will include an adapted version of the NHS Friends and Family Test, questions on satisfaction, possible negative/adverse experiences, possible positive experiences, and an option for free text comments at the end of the survey.

Qualitative work will focus on two groups: (a) dental professionals (incl. triage, in-practice dental teams, CDS teams and referring practices) and (b) patients (incl. parents and children) accessing and using CFDPs.

(a) Dental teams' attitudes and beliefs regarding CFDP will be examined to better understand what worked well, what created barriers and look at how best to support implementation for such initiatives if they become routine practice.

In a qualitative approach, we will explore dental team beliefs, attitudes, and opinions regarding CFDPs and traditional pathways. To allow for the realist evaluation to take place, a combination of focus groups and one-to-one interviews will take place with the triage team and staff at CFDPs.

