Summary descriptive data will be reported by study arm and overall using tables of frequencies or means and standard deviations as appropriate to characterise the population and identify any imbalance between groups. The comparison of outcomes from the traditional specialist dental service route (control) compared to the intervention treatment under the alternative Child-Friendly Dental Practice will be assessed to determine if there are clinically meaningful and statistically significant differences in key outcomes. The primary outcome is receipt of GA for tooth extraction within two years of initial referral. Referral along both pathways may still result in the need for a GA for some children but a key metric will be to determine whether there

is a meaningful difference in the number of GAs per referral pathway. The primary outcome will be analysed using a mixed effects logistic regression model, accounting for the traditional specialist dental service route or alternative Child-Friendly Dental Practice, with random effects for centre. An adjusted logistic regression analysis additionally accounting for the age, deprivation, ethnicity, sex of the child along with the number of teeth requiring treatment at initial examination (through the CFDP or CDS) will also be undertaken. The analysis dataset will include all participants for whom there is follow-up data from the NHS BSA and the baseline covariates.

Analysis of secondary outcomes will be undertaken in a similar manner using covariate adjusted linear or logistic regression models as appropriate, we will include the modifying effect of deprivation

The health economics analysis will adopt a cost-consequences approach whereby the costs of each pathway will be presented separately but alongside relevant outcomes: 1) dental extractions under GA, 2) count of children who are successfully seen and treated in each pathway, 3) count of treatments performed (extractions, restorations), 4) mean wait time and 5) dental pain experienced by a child. Resource use and costs from the CFDP pathway will also be used in a budget impact analysis. Differences in outcomes will be generated from the quantitative analysis.

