FILLED_PERM	Number of filled permanent teeth (in DMFT component). This is part of the DMFT index
FILLED_PERM_COUNT	If the Filled component was completed or not. N=0, 1=Y. This is part of the DMFT index
FISSURE_SEALMENTS	
FISSURE_SEALMENTS_COUNT	
FLOURIDE_VARNISH_COUNT	
INLAYS	
INLAYS_COUNT	
MISSING_PERM	Number of missing permanent teeth . This is part of the DMFT index
MISSING_PERM_COUNT	if the M component was completed or not (0=N, 1 =Y). This is part of the DMFT index
RADIOGRAPHS	Number of radiographs taken (will only be from 2015 as not in legacy data)
RADIOGRAPHS_COUNT	If rads were taken or not (N=0, Y=1)
SCALE_POLISH_COUNT	
EXTRACTIONS_COUNT	If extractions were carried out

EXTRACTIONS	How many extractions
PERM_FILL_COUNT	If fillings were carried out. 0=NO, 1-Y
PERM_FILL	Number of permanent fillings and / or sealant restorations provided
RECALL_COUNT	Was a recall interval completed? Y=1, N=0
RECALL_INTERVAL	What is the recall interval? (3,6,12,18,24 months)
LAST_TREATMENT_DATE	This is date of last CoT
NUM_PERFORMERS	Total number of unique performers that the patient has seen over the 10 years. (Will be the same number in each row)
NUM_PRACTICES	Total number of different practice addresses the patient has attended over th 10 years.
DECAYED_deciduous	Decayed deciduous. This is part of the dmft index number of decayed teeth.
DECAYED_deciduous_COUNT	This is part of the dmt index f they completed the Decayed (deciduous) componenent. 0=N and 1=Y
FILLED_deciduous	Number of filled deciduous teeth (in dmft component). Double check this isn't fillings carried out. This is part of the DMFT index
FILLED_deciduous_COUNT	If the Filled (deciduous) component was complet dmfted or not. N=0, 1=Y. This is part of the DMFT index
MISSING_deciduous	Number of missing deciduous teeth . This is part of the dmft index
MISSING_deciduous_COUNT	if the M (deciduous) component was completed or not (0=N, 1 =Y). This is part of the dmft index
Sedation	Sedation
Treatment on referral	Treatment on referral
Further treatment within 2 months –	Further treatment within 2 months –

HES NHS digital CDS data

Link using DOB Name, URN NHS number	PANDA ID	dental GA (yes no)	Date of referral for DGA	Date of dental GA (if occurred)
-------------------------------------------	----------	--------------------	--------------------------	------------------------------------

Referral form data

Patient complaint	free text
-------------------	-----------

Reason for urgent care	free text

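### The primary outcome counts only general anaesthetics received within two years, so a child still queuing for one at 24 months is coded as never having needed it

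*Protocol*

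**What the plan says.** The Outcomes section defines the primary outcome as a yes/no variable that "measures whether a child has had a dental extraction under General Anaesthetic two years after referral as indicated in electronic patient records". Section X (Data analyses) repeats this: "The primary outcome is receipt of GA for tooth extraction within two years of initial referral". It adds that "The primary outcome will be analysed using a mixed effects logistic regression model". Neither place says how to treat a child who has been referred for GA but not yet treated.

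The Sample size section uses a different word for the quantity of interest: "a difference in proportions in the need for a GA from 25% to 15% to be detected".

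The Rationale reports GA waits of up to 12 months before Covid-19 and, for December 2021, "1779 children on the waiting list, 716 of whom have been waiting over 52 weeks". It then says the numbers are falling. It also records the worry that "children treated within a CFDP may still require future intervention in a more specialist service, within a short period of time".

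Two other items bear on the point. A secondary outcome counts children who return to the specialist pathway within two years of referral. Appendix B, in the table for HES, NHS Digital and CDS data, lists a field "Date of referral for DGA" next to the date of the GA itself. No stated outcome uses the referral date.

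**The concern.** Receipt of a GA on a fixed clock depends on need and on how fast the queue moves. The clock starts at the initial referral in both arms. A CDS child is already in the specialist pathway. A CFDP child who turns out to need a GA first uses up time waiting for and attending the CFDP. If the remaining steps are the same, fewer of the needed GAs in the CFDP arm fall inside 24 months, even when need is identical.

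The primary comparison would then mix GAs avoided with GAs deferred. The Rationale gives that distinction as a reason for the study: if children later need specialist care, pressure does not fall and total cost rises. The cost-consequences analysis uses extractions under GA over the same two-year horizon, so deferred GAs would also drop out of it. The Risks and benefits section says the scheme will continue, expand or cease on the result.

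**Working it through.** **1. The plan's own figure.** Inputs from the Sample size section: 25% v 15%, two-sided 0.05, 90% power. With a pooled mean of 0.20:

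n = [1.960·√(2·0.20·0.80) + 1.2816·√(0.25·0.75 + 0.15·0.85)]² / 0.10² = (1.1087 + 0.7193)² / 0.01 ≈ 334.2, so 335 per group.

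With the continuity correction, n′ = (n/4)·[1 + √(1 + 4/(n·0.10))]² ≈ 354. This matches the plan, so the arithmetic is not in question. The issue is that 25% and 15% are labelled as need while the variable recorded is receipt.

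**2. What the coding does.** Observed rate = need × (1 − share of needed GAs outstanding at 24 months). The documents give no such share, so these are assumptions, with need 25% in both arms:

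- 20% outstanding in both arms: 20.0% v 20.0%, no false difference.
- 10% in CDS, 30% in CFDP: 22.5% v 17.5%, a false 5 points. The chance of a significant result favouring the CFDP at 354 per group is about 38%, against a nominal 2.5%.
- 0% in CDS, 40% in CFDP: 25.0% v 15.0%, the whole design effect.

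Only the difference between the arms matters.

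**3. How a difference could arise.** Waits were simulated as gamma (shape 2), with need 25% in both arms and complete 24-month records. Time to GA in CDS = specialist stage + GA wait. Two routes were tried for the CFDP:

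- full chain: CFDP stage + specialist stage + GA wait;
- direct: CFDP stage + GA wait.

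All mean waits are assumptions.

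| Mean months: CFDP / specialist / GA | CDS received | CFDP received, full chain | False difference, full chain (points) | False difference, direct (points) |
|---|---|---|---|---|
| 4 / 3 / 6 | 24.8% | 24.0% | 0.8 | 0.2 |
| 4 / 3 / 9 | 23.6% | 21.7% | 1.8 | 0.4 |
| 6 / 4 / 12 | 20.9% | 16.1% | 4.8 | 1.5 |
| 6 / 6 / 15 | 16.8% | 11.6% | 5.2 | about 0 |
| 2 / 6 / 9 | 22.0% | 20.8% | 1.2 | −1.9 |

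Differences are CDS minus CFDP, taken from unrounded rates. For the first four full-chain rows, the chance of a significant false result favouring the CFDP at 354 per group is about 4%, 9%, 38% and just over 50%.

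**4. Does counting listed children help?** If a child performed or listed for GA by 24 months counts as an event, the full-chain false difference falls from 4.8 to about 0.4 points (6/4/12) and from 5.2 to about 1.0 (6/6/15). The remainder is children sent on but not yet listed for GA at 24 months.

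**The case against.** A reader might infer that the bias certainly favours the CFDP. The documents do not support that. They speak of children returning to the specialist pathway, but not of whether such a child repeats the specialist wait or goes straight to the GA list. Under the direct route the false difference is small, absent or reversed, and the scheme is meant to give quicker access than an overloaded CDS. This objection stands, and it limits the point to a conditional one.

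A reader might also take 716/1779 = 40.2% as the share outstanding. It is a December 2021 snapshot of waits over 52 weeks, not 24 months. It is not stated to be limited to study-eligible children, and the protocol says the numbers are falling. It shows that queues can be long relative to the window, but it does not size the bias.

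Nor would it be right to say that deferred and avoided GAs cannot be told apart. The two dates in Appendix B can largely separate them; the stated outcome does not use them.

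Receipt also matches the research question, which asks about GA treatment over two years, so the primary outcome need not be replaced. The secondary outcome on return to the specialist pathway exposes part of the problem. However, it counts any return rather than GA listing and has no direct CDS counterpart, so it does not correct the between-arm GA comparison. Supporting analyses may sit in a statistical analysis plan that is not shown. The mismatch between need and receipt, however, is in the protocol itself.

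**Conclusion.** The coding problem is certain on the text: a child waiting for GA at 24 months counts as no GA in either arm, while the sample size speaks of need. The direction and size of any bias are not certain. It favours the CFDP only if CFDP children who need a GA have the larger backlog at 24 months, which is plausible but undocumented. With equal 25% need, the assumed full-chain waits give about 1 to 5 points against a 10-point target. The direct route gives between 1.5 points in favour of the CFDP and 1.9 against it. All of this rests on assumed waits and on complete two-year records. Moderate severity: a cheap improvement, not a reason to change the primary outcome.

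**What to change.** Keep GA received within two years as the primary outcome, and align the wording of the sample size with it.

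Prespecify one key supporting analysis, with an estimate and confidence interval: *GA performed, or referred for dental GA and still waiting, by 24 months from referral*. Derive it in both arms from the GA referral date and the GA date in Appendix B. Report by arm the number still waiting for GA at 24 months, and the number referred back to the specialist pathway but not yet seen, since the supporting outcome misses the latter. State that a lower GA rate will be read as GA avoided, rather than deferred, only in the light of that estimate and its interval. Mere agreement in sign would be too weak a rule, because it asks for no precision.

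The cost is a few lines of wording and one further analysis on fields already listed. Confirm that the GA referral date can be obtained for the unconsented CFDP children, whose linkage is described only through NHS England and NHS BSA. The downside is that some listed children never have the GA, so the supporting outcome slightly overstates GA use.
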